****Every attempt should be made to make the cardiac exposure to radiation as low as possible.**

7.5 Radiation Therapy Quality Assurance

Submission of treatment plans in digital format as DICOM RT is required. Digital data must include CT scans, structures, plan and dose files. This study uses TRIAD for RT data submission. Use of TRIAD requires several preliminary steps. See [Section 4.2.](#) for details. Additional information is available at:

In the event that a site has not completed all steps required for TRIAD data submission in time to meet the timeline for review, data submitted via SFTP will also be accepted. See the instructions for submission of data via SFTP on the IROC Rhode Island website under Digital Data.

Any items listed below that are not part of the digital submission may be included with the transmission of the digital RT data.

All required data should be submitted within 3 days of the start of radiotherapy for on-treatment review. In the event that a site submits plans for two or more cases requiring major revisions or having unacceptable deviations, the site may be asked to submit plans prior to treatment for subsequent patients.

Within 3 days of the start of radiotherapy, the following data should be submitted for on-treatment review:

7.5.1 Treatment Planning System Output

- RT treatment plan including CT, structures, dose, and plan files. These items are included in the digital plan.
- Dose volume histograms (DVH) of the GTV, chest wall, heart. When using IMRT, a DVH shall be submitted for a category of tissue called “unspecified tissue.” This is defined as tissue contained within the skin, but which is not otherwise identified by containment within any other structure. DVH’s are included in the digital plan.
- Digitally reconstructed radiographs (DRR) for each treatment field. Please include two sets, one with and one without overlays of the target volumes and organs at risk. Submission of DRR’s is not required for IMRT.
- Treatment planning system summary report that includes the monitor unit calculations, beam parameters, calculation algorithm, and volume of interest dose statistics.

7.5.2 Supportive Data

The following data is to be submitted to IROC Rhode Island:

- Copies of operative & pathology reports for mastectomy/SLN/ALND/Plastic Surgery procedures.
- Prescription sheet for entire treatment.
- If the recommended doses to the organs at risk are exceeded, an explanation should be included for review by IROC Rhode Island and the radiation oncology reviewers.

7.5.3 Forms

The following forms are to be submitted to IROC Rhode Island:

- RT-1 Dosimetry Summary Form

Within 21 days of the completion of radiotherapy, the following data shall be submitted for all patients:

- The RT-2 Radiotherapy Total Dose Record Form
- A copy of the patient's radiotherapy record including the prescription, and the daily and cumulative doses to all required areas.
- Documentation listed above showing any modifications from the original submission.

Supportive data and forms may be included with the transmission of the digital RT data or submitted separately via e-mail [REDACTED]

Questions regarding the dose calculations or documentation should be directed to:

[REDACTED]
[REDACTED]
[REDACTED]
[REDACTED]

7.5.4 Definitions of Deviations in Protocol Performance

Per protocol: All specified DVH requirements identified as "Preferred" have been met.

Variation Acceptable: Specified DVH requirements within the “Acceptable” range have been met.

Deviation Unacceptable: Specified DVH requirements for Variation Acceptable are not met.

7.5.5 Definitions of Deviations in Volumes Drawn

Per protocol: All specified contouring volumes are drawn as specified in the protocol.

Variation Acceptable: Delineation of specified contouring volumes deviates from protocol guidelines but the protocol intended volumes are adequately covered by the prescribed doses.

Deviation Unacceptable: Delineation of specified contouring volumes deviates significantly from protocol guidelines and the protocol intended volumes are not adequately covered by the prescribed doses.

8.0 DOSE AND TREATMENT MODIFICATIONS

Radiation doses should not be modified and compliance with the protocol will be determined as defined above, by the ideal and acceptable dose constraint criteria. Patients may occasionally require treatment breaks, which should be kept to a minimum. Treatment breaks of up to 5 treatment days will be considered acceptable. Treatment breaks of greater than 5 treatment days are strongly discouraged.

9.0 ADVERSE EVENTS

The prompt reporting of adverse events is the responsibility of each investigator engaged in clinical research, as required by Federal Regulations. Adverse events must be described and graded using the terminology and grading categories defined in the NCI's Common Terminology Criteria for Adverse Events (CTCAE), Version 4.0. However, CTCAE v5.0 must be used for serious AE reporting through CTEP-AERS as of April 1, 2018. The CTCAE is available at [REDACTED]

Attribution to protocol treatment for each adverse event must be determined by the investigator and reported on the required forms. Please refer the NCI Guidelines: Adverse Event Reporting Requirements for further details on AE reporting procedures. Radiation-related CTCAE toxicity assessment will be assessed as a secondary endpoint in both acute and late affects.

9.1 Routine Adverse Event Reporting

Adverse event data collection and reporting, which are required as part of every clinical trial are done to ensure the safety of patients enrolled in the studies as well as those who will enroll in future studies using similar agents. Adverse events are reported in a routine manner at scheduled times according to the study calendar in Section 5.0. For this trial, Solicited Adverse Event Solicited form is used for routine AE reporting in Rave.

Acute Adverse Events: Acute adverse events, will be scored per CTCAE 4.0 regardless of attribution. Attribution will however be collected for separate analysis.

Late Radiation Adverse Events: Late radiation complications will be defined as those that are present ≥ 6 months after the final dose of radiation and include CTCAE 4.0 grade 3+:

9.2 Solicited Adverse Events:

The following adverse events are considered "expected" and their presence/absence should be solicited, and severity graded, at baseline and for each cycle of treatment.

9.2.1 Radiation Therapy Complications:

CTCAE v4.0 Term	CTCAE v4.0 System Organ Class (SOC)
Fibrosis, deep connective tissue	Musculoskeletal and connective tissue disorders
Superficial soft tissue fibrosis	Musculoskeletal and connective tissue disorders
Chest wall pain	Musculoskeletal and connective tissue disorders
Joint range of motion decreased	Musculoskeletal and connective tissue disorders
Wound Infection	Infections and infestations
Fatigue	General disorders and administration site conditions
Dermatitis radiation	Injury, poisoning and procedural complications
Wound complication	Injury, poisoning and procedural complications
Wound dehiscence	Injury, poisoning and procedural complications
Lymphedema	Vascular disorders
Telangiectasia	Skin and subcutaneous tissue disorders
Hypothyroidism	Endocrine Disorders
Myocardial Infarction	Cardiac disorders
Cardiac disorders – Other specify*	Cardiac disorders
Pulmonary fibrosis	Respiratory, thoracic and mediastinal disorders
Brachial Plexopathy	Nervous system disorders
Peripheral motor neuropathy	Nervous system disorders
Peripheral sensory neuropathy	Nervous system disorders
Treatment related secondary malignancy	Neoplasms benign, malignant and unspecified (including cysts and polyps)

* Specific cardiac events, if and when they occur will be recorded on the Adverse Events: Other form.

9.2.2 Non CTCAE RT Associated Complications:

- a) Shoulder stiffness (occasional) (Grade 1-3)
- b) Rib fracture (rare) (Grade 1-3)

9.2.3 Non CTCAE Reconstruction Associated Complications:

The primary endpoint of this trial is the reconstruction complication rate at 24 months after radiation that requires hospitalization or re-operation. (Complications related to the contralateral breast will be collected but will not count towards the assessment of the primary endpoint, ipsilateral breast complications will be counted towards the primary endpoint). This is an adverse event rate not well characterized by the CTCAE terminology, and therefore will be recorded separately from CTCAE toxicity as follows:

- a. Capsular contracture (Baker grades III-IV would only count towards the primary endpoint)
Definition of Capsular contracture grades (to be captured in Rave)
 - Grade I — the breast is normally soft and appears natural in size and shape
 - Grade II — the breast is a little firm, but appears normal
 - Grade III — the breast is firm and appears abnormal
 - Grade IV — the breast is hard, painful to the touch, and appears abnormal
- b. Complete failure of the implant/skin flap
- c. Unplanned admission for reconstruction related issue(s) including but not limited to infection, wound healing complication or pain
- d. Unplanned return to the operating room for reconstruction related issue including but not limited to infection, prosthesis exposure, failed reconstruction, implant removal, wound healing complications or contracture management

Routine revisions, such as dog-ear corrections, fat grafting and revising the contralateral breast will not be scored as an adverse reconstruction event. Additionally, a contracture that is corrected when the tissue expander is exchanged for an implant or autologous tissue flap will not be scored as an event.

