1.0 BACKGROUND

In the last 5-10 years, there has been a significant shift in the radiation of women with intact breast cancer to shorter, more cost effective and convenient treatment courses. Through the work of several prospective published trials, this concept has been found to be safe and effective in women undergoing breast conserving therapy.[1-4] Decreasing the time required for women to undergo post mastectomy radiation decreases health care costs, and allows patients to spend more time out side of the healthcare setting, ultimately improving patient, employer and payer satisfaction. As the outcomes with traditional post mastectomy are already considered safe and effective, this trial is designed as a non-inferiority trial to ensure that a shorter time course of radiation is as safe as the current standard of care. Although there are limited data from Europe that support this concept in mastectomy and regional nodal irradiation (RNI) patients, no studies have been done in the setting of breast reconstruction. We need prospective randomized data using modern radiotherapy and chemotherapy before widespread adoption occurs here in the United States and elsewhere. Post Mastectomy Radiation Therapy (PMRT) in this setting is a combination of all hypofractionation challenges, combining concerns over adjuvant chemotherapy, post mastectomy chest wall, supraclavicular fossa, internal mammary nodes and reconstructed breast short course radiation. Each of these factors independently is a potential contraindication to hypofractionated radiation due to a lack of data. There are two pressing and currently outstanding questions related to hypofractionation that require resolution in a phase III setting:

- 1) What is the rate of radiation related complications in reconstructed chest walls treated with shortened course radiotherapy?
- 2) Is hypofractionation safe when treating regional nodal volumes (where the brachial plexus is located)?

These two questions have been contentious, and their uncertainty will directly affect patient care for years to come, unless a well-designed study can define the unknowns. In this study, both of these questions will be tested and resolved as primary and secondary endpoints. This trial design also collects much needed prospective data regarding the true complication rates for PMRT with breast reconstruction, given the multitude of options for breast reconstruction timing and techniques.

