9.3 CTCAE Routine Reporting Requirements

In addition to the solicited adverse events listed in Section 9.1, the following table outlines the combinations of time points, grades and attributions of AEs that require routine reporting to the Alliance Statistics and Data Center. Attribution refers to radiation and reconstruction. Adverse events attributed to chemotherapy need not be reported. Questions about routine reporting should be directed to the Data Manager.

*Combinations of CTCAE Grade & Attribution Required for Routine AE Data Submission on Case Report Forms (CRFs)

Attribution	Grade 1	Grade 2	Grade 3	Grade 4	Grade 5
Unrelated			a	a	a
Unlikely			a	a	a
Possible	a	a	a, b	a, b	a, b
Probable	a	a	a, b	a, b	a, b
Definite	a	a	a, b	a, b	a, b

- a) Adverse Events: Other CRF - Applies to AEs occurring between registration and within 30 days of the patient's last treatment date, or as part of the Clinical Follow-Up Phase.
- b) Adverse Events: Late CRF - Applies to AEs occurring greater than 30 days after the patient's last treatment date.

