 - “10 calendar days” - A complete CTEP-AERS report on the AE must be submitted ≤ 10 calendar days of the investigator learning of the event.
- Any medical event equivalent to CTCAE grade 3, 4, or 5 that precipitates hospitalization (or prolongation of existing hospitalization) must be reported regardless of attribution and designation as expected or unexpected with the exception of any events identified as protocol-specific expedited adverse event reporting exclusions (see below).
- Any event that results in persistent or significant disabilities/incapacities, congenital anomalies, or birth defects must be reported via CTEP-AERS if the event occurs following treatment with an agent under a CTEP IND.
- Use the NCI protocol number and the protocol-specific patient ID provided during trial registration on all reports.

Additional Instructions or Exclusion to CTEP-AERS Expedited Reporting Requirements for Phase 2 and 3 Trials Utilizing an Agent Under a CTEP IND or non-CTEP IND:

- All adverse events reported via CTEP-AERS (i.e., serious adverse events) should also be forwarded to your local IRB.
- Adverse events attributed to chemotherapy need not be reported.
- Grade 1-3 nausea or vomiting and hospitalization resulting from such do not require AERS reporting, but should be reported via routine AE reporting.
- Grade 3 or 4 nausea or vomiting does not require AERS reporting, but should be reported via routine AE reporting.
- Grade 1-3 fatigue and hospitalization resulting from such do not require AERS reporting, but should be reported via routine AE reporting.
- Grade 3 or 4 fatigue does not require AERS reporting, but should be reported via routine AE reporting.

- Grade 1-3 radiation dermatitis and hospitalization resulting from such do not require AERS reporting, but should be reported via routine AE reporting.
- Grade 3 or 4 radiation dermatitis does not require AERS reporting, but should be reported via routine AE reporting
- Grade 1-3 lymphedema and hospitalization resulting from such do not require AERS reporting, but should be reported via routine AE reporting.
- Grade 3 lymphedema does not require AERS reporting, but should be reported via routine AE reporting
- Grade 1-3 pneumonitis and hospitalization resulting from such do not require AERS reporting, but should be reported via routine AE reporting.
- Grade 3 or 4 pneumonitis does not require AERS reporting, but should be reported via routine AE reporting

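### Pneumonitis is moved from expedited to routine reporting but is not a solicited term, so it is captured only as an unprompted event, and grade 1-2 events judged unrelated or unlikely need not be submitted

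*Combined protocol and SAP*

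**What the plan says.** Section 9.4 lists protocol-specific exceptions to expedited (CTEP-AERS) reporting. Two concern pneumonitis: "Grade 1-3 pneumonitis and hospitalization resulting from such do not require AERS reporting, but should be reported via routine AE reporting" and "Grade 3 or 4 pneumonitis does not require AERS reporting, but should be reported via routine AE reporting".

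Section 9.1 names the form for routine reporting: "For this trial, Solicited Adverse Event Solicited form is used for routine AE reporting in Rave". Section 9.2 says of the listed events that "their presence/absence should be solicited, and severity graded, at baseline and for each cycle of treatment". The table in 9.2.1 has 19 CTCAE terms. The one respiratory term is "Pulmonary fibrosis". Pneumonitis is not in that table, nor among the non-CTCAE items in 9.2.2.

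Section 9.3 adds a second route: "In addition to the solicited adverse events listed in Section 9.1, the following table outlines the combinations of time points, grades and attributions" of events that must be submitted. It uses two forms, Adverse Events: Other and Adverse Events: Late.

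Sections 9.1 and 10.2 both score acute adverse events under CTCAE 4.0 whatever their attribution, and both limit late radiation complications to grade 3 or higher at six months or more after radiation. Section 12.4.1 compares the proportion of patients with acute or late radiation complications between arms.

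**The concern.** The sponsor foresaw pneumonitis well enough to write exemptions for it, including one covering hospitalization. The exemption leans on routine reporting, yet the form that 9.1 names for that purpose does not list the event. For a solicited term, the protocol requires that presence or absence be asked and graded. For pneumonitis, a blank may mean that the patient did not have it or that nobody asked.

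This matters because acute and late CTCAE toxicity is a secondary comparison in an unblinded trial. Events that depend on recognition and attribution by staff who know the arm are more open to uneven ascertainment than events asked about by name at each visit. With expedited reports waived, routine data are also the main source on pneumonitis for the six-monthly DSMB reports (12.7.1). Both arms treat the internal mammary and supraclavicular nodes, and 7.4.3 sets lung dose limits in each arm, so a reader of the results will reasonably look for a pneumonitis figure.

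**Working it through.** The plan states no figure for this point, so the check compares the passages.

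**Is pneumonitis solicited?** No. I counted 19 terms in 9.2.1. Pulmonary fibrosis is the only one in the respiratory class.

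**Is that usual for the exempted events?** Mostly not. Of the events exempted in 9.4, fatigue, radiation dermatitis, lymphedema, myocardial infarction and wound infection are all named in 9.2.1. Nausea and vomiting, like pneumonitis, are exempted but not listed.

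**What does 9.3 require for an unlisted event?** The table crosses 5 attribution levels with 5 grades, giving 25 cells.
- Grade 3-5, any attribution: 3 × 5 = 15 cells required.
- Grade 1-2, possible, probable or definite: 2 × 3 = 6 cells required.
- Grade 1-2, unrelated or unlikely: 2 × 2 = 4 cells not required.
- Total required: 15 + 6 = 21 of 25.

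Section 9.3 also excuses events attributed to chemotherapy.

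**Do 9.1 and 9.3 agree?** Not for acute events. Section 9.1 scores them whatever their attribution; 9.3 does not require the four low-grade cells. A solicited term such as fatigue is recorded at grade 1-2 with no attribution filter stated. An unlisted term such as pneumonitis at the same grade can be left out once it is rated unrelated or unlikely.

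**Does timing leave a further weak spot?** The Late form covers events more than 30 days after the last treatment, and only related grade 3-5 events. A related grade 1-2 event after day 30 must rely on the clause that extends the Other form to the clinical follow-up phase. The 2-to-8-week visit (14 to 56 days) straddles that line.

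**Which analyses can the attribution filter reach?**
- Acute comparison in 12.4.1: yes, through grade 1-2 events.
- Late comparison in 12.4.1: no, because late complications are grade 3 or higher.
- Stopping counts in 12.7.2: no. They use grade 3 or higher, or grade 4 or higher, events at least possibly related to treatment, and all of those cells are required.

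**Is 9.4 consistent on grade 4?** No. One bullet exempts grade 3 or 4 pneumonitis. Near its end, the same section requires CTEP-AERS reports for grade 4 toxicities that reflect life-threatening events. Deaths stay expedited whatever the cause.

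**The case against.** The strongest reply is that routine reporting consists of 9.1 and 9.3 together, so the exemption in 9.4 has a working destination. Submission under 9.3 is required, not optional. The footnote to 9.2.1 itself sends specific cardiac events to the Other form, so that form is an intended route. Calendar footnote A has radiation side effects assessed from the history and physical, at visits from before radiation to five years. Which terms to solicit is partly a matter of preference.

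Most of this stands, and it rules out several stronger readings:
- A reader might infer that pneumonitis is recorded only if a site chooses to volunteer it. Section 9.3 contradicts that; what is missing is the prompt, not the duty to report.
- A reader might infer that no negative answer can ever be recorded. The case report forms are not in the documents, so this cannot be confirmed.
- A reader might infer that the attribution filter weakens the 12.7.2 stopping counts. It cannot, as shown above.
- A reader might treat pneumonitis as the main early lung harm of nodal radiation. The documents do not say so, and the nodal safety question in section 1.0 is framed around the brachial plexus, for which plexopathy is solicited.
- A reader might put a figure on lost power. The documents give no pneumonitis rate and no capture rate, and 12.4.1 specifies no pneumonitis test.

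The reply does not remove two things. A general instruction to assess side effects is not a question about a named event, and 9.1 and 9.3 still disagree on grade 1-2 acute events.

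**Conclusion.** The point holds as a gap in ascertainment. Pneumonitis is anticipated in 9.4, is absent from the solicited terms in 9.2.1, and so is captured unprompted under 9.3. Four of 25 grade-by-attribution cells, all grade 1-2 and rated unrelated or unlikely, need not be submitted, against the rule in 9.1 for acute events.

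The effect is confined to the secondary toxicity comparison and safety review; the primary endpoint is untouched. Its size in event rates cannot be stated from the documents. The practical consequence is that a low pneumonitis count, particularly at grade 1-2, could not be read with confidence as absence of the event in either arm. This assumes that the Solicited form follows the 9.2.1 list. If the form already prompts for pneumonitis, only the textual conflicts remain.

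This is a cheap improvement, not a flaw that threatens the trial's main conclusion.

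**What to change.** - Add pneumonitis (Respiratory, thoracic and mediastinal disorders) to the 9.2.1 table and to the Solicited form, asked and graded at every adverse event visit in the study calendar.
- Tabulate it by grade and arm alongside the 12.4.1 complications.
- Align 9.3 with 9.1 so that acute events are submitted whatever their attribution, with attribution kept as a recorded field for the separate analysis that 9.1 already foresees.
- Reconcile the two statements in 9.4 on expedited reporting of grade 4 events.

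The cost is one row on an existing form, one row in a toxicity table and one more item per visit. The calendar has 11 adverse event visits to five years (before radiation; at completion; 2 to 8 weeks; 6, 12 and 18 months; 2 years; 30 months; 3, 4 and 5 years: 1 + 1 + 1 + 3 + 1 + 1 + 3), so at most 11 extra answers per patient. No new visit or test is needed. Aligning 9.3 also means that sites submit some low-grade acute events that they may now omit.
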